Daily study treatment will begin on C1D1. Cycles are 28 days (± 2 days) in duration and dosing is continuous. All subjects will continue to receive best supportive care according to institutional practice throughout the study. Study visits will be conducted every week during Cycle 1 (Days 1, 8, 15, and 22), and every other week during Cycles 2 and 3, and Day 1 of each cycle thereafter.

An End of Treatment (EOT) Visit will be performed on the last day of study treatment (within 5 to 33 days of last dose, to accommodate for potential dosing delays of up to 28 days).

Radiographic assessment (CT or MRI) for evaluation of disease response will be conducted every 6 weeks (± 5 days) for the first 8 assessments (i.e., through week 48) and every 8 weeks (± 5 days) thereafter from C1D1, independent of dose delays and/or dose interruptions, and/or at any time when progression of disease is suspected. For subjects who discontinue study drug

for reasons other than disease progression, than withdrawal of consent, or start of another anticancer agent, an assessment will be conducted at the EOT Visit.

Upon radiographic disease progression, PIs, with consult from the Sponsor, may keep the subjects on ivosidenib after the disease progression provided the subject is clinically benefitting and there is no contraindication to continuing treatment beyond progression (see [Section 8.10.1.2](#)). Target and non-target lesion selection and objective tumor response assessments per Response Evaluation Criteria in Solid Tumors (RECIST) v1.1 will be performed by the Investigator(s). An independent central review of response will be conducted by an Independent Radiology Center (IRC) per RECIST v1.1. All scans will be sent to the IRC as detailed in the site-specific Imaging Core Manual (see [Section 7.2.1](#)). HRQOL assessments will be conducted pre-dose on C1D1 and on Day 1 of every cycle thereafter until EOT. After EOT visit, the HRQOL will be conducted every 12 weeks until the start of new anticancer therapy. One additional HRQOL assessment will also be conducted at the safety follow-up visit. Health economic outcomes assessments will occur pre-dose on C1D1 Cycle 3, Day 1 (C3D1), and at the EOT visit. Compliance assessments will occur at Cycle 2, Day 1 (C2D1), Day 1 of every cycle thereafter, and at the EOT Visit.

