#### 5.3.1. Primary efficacy endpoint

The primary analysis will be performed on the ITT set.

The progression-free survival (PFS) by IRC is defined as the time in months from Day 1 (C1D1) to the date of the first documentation of disease progression as determined by the IRC per RECIST v1.1 or death due to any cause, whichever occurs first.

PFS = (Earliest Date of Disease Progression or Death – Day 1 Date + 1) / 30.4375.

The primary endpoint is PFS status at 6 months after Day 1 (C1D1). The 6-month PFS rate defined as the probability of subjects who are alive and progression-free at 6 months after Day 1 (C1D1) will be used to assess the primary endpoint. Kaplan-Meier method will be used to estimate the 6-month PFS rate. Exact binomial test with 1-sided significance level of 0.05 will be used to compare the 6-month PFS rate against 2.6%.

Subjects without documentation of disease progression or death at the time of the analysis of PFS will be censored at the date of the last response assessment prior to the start of alternate therapy. See [Table \(5.3.1\) 1](#) for the details on handling of missing response assessments and censoring.

Number of subjects with events, types of events (progression or death), and number of subjects censored, number of subjects for each reason of censoring, Kaplan-Meier estimates, and 95% CIs according to Brookmeyer and Crowley method for the median, Q1 and Q3 for PFS will be presented. Probabilities of event free at selected time points, such as 3-month, 6-month, 9-month, and 12-month, will be presented. Kaplan-Meier curves of PFS will be provided with the number of subjects at risk over time included.

In addition, the concordance of PFS between investigator and IRC assessment will also be summarized.

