**Table (5.3.1) 1 Handling of Missing Response Assessment and Censoring for the Primary Analysis of PFS**

Situation	Date of Censoring
No baseline assessment and no death.	Date of the Cycle 1 Day 1
Alternate anticancer systemic treatment started before documented progression (PD) per RECIST 1.1 or death.	Date of last adequate assessment prior to the start of alternate anticancer treatment 
No adequate post-baseline assessment and no death.	Date of the Cycle 1 Day 1
No documented PD per RECIST 1.1 or death before data cut-off date or before permanently discontinued from the study.	Date of last adequate assessment 

Situation	Date of Censoring
Documented PD per RECIST 1.1 or death following a long gap from the previous adequate assessment (e.g., 2 or more consecutive missed scheduled disease status assessments). The long gap is defined as $\geq 95$ days (ie, 12 weeks + 10 days per the protocol defined visit window). If no adequate assessment prior to minimum of (PD, death), the long gap is calculated from the Cycle 1 Day 1.	Date of last adequate assessment prior to the first occurrence of 2 or more consecutive missing scheduled assessments

 Adequate disease assessment is defined as a response assessment other than “not evaluable.” If there is no adequate response assessment prior to the start of anticancer treatment, it will be censored at the date of Cycle 1 Day 1.

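### The 95-day long-gap limit for censoring PFS fits the 6-weekly scans only; after Week 48 one missed scan can meet it, and the row's two columns then disagree

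*SAP*

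**What the plan says.** The last row of SAP Table (5.3.1) 1 censors a progression or death that comes after a long gap from the previous adequate assessment.

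- **Situation column.** The gap is illustrated, after an e.g., by "2 or more consecutive missed scheduled disease status assessments". The next sentence defines it as 95 days or more, "ie, 12 weeks + 10 days per the protocol defined visit window". If there was no adequate assessment, the gap runs from C1D1.
- **Date column.** The censoring date is "Date of last adequate assessment prior to the first occurrence of 2 or more consecutive missing scheduled assessments".
- **Footnote 1.** "Adequate disease assessment is defined as a response assessment other than" not evaluable. The footnote mark sits on two other rows, not on this one.

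Protocol Section 4.1.1 schedules scans every 6 weeks (± 5 days) for the first 8 assessments, through Week 48, then "every 8 weeks (± 5 days) thereafter from C1D1". Scans are also required "at any time when progression of disease is suspected". The SAP gives no second limit for the 8-weekly period.

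SAP Sections 5.3.2.2 and 5.3.2.4 apply the same censoring rules to Investigator PFS and to duration of response (DoR).

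**The concern.** A limit built from two 6-week intervals separates one missed scan from two only while scans are 6-weekly. On the 8-weekly schedule one missed scan is enough to reach it. The situation column then says the row applies, while the date column needs two missing assessments in a row and so supplies no date. One programmer could follow the day definition and censor the event. Another could follow the count and keep it.

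The choice bears on outputs that SAP Section 5.3.1 promises: the event count, "number of subjects censored, number of subjects for each reason of censoring", the Kaplan-Meier curve, and "Probabilities of event free at selected time points, such as 3-month, 6-month, 9-month, and 12-month, will be presented". With about 10 subjects, one reclassified event is visible in each of these.

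**Working it through.** **The plan's own figure.** 12 weeks + 10 days = 84 + 10 = 94 days, so the first day beyond it is day 95. The stated limit reproduces.

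**Gap to the next scheduled scan after one missed scan.** Each scan may fall ± 5 days from its nominal day, counted from C1D1, so the gap is the nominal interval ± 10 days, with 11 × 11 = 121 window combinations.

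| Last adequate scan, missed scan, PD scan | Nominal gap | Range | Combinations at 95 days or more |
|---|---|---|---|
| 6-weekly, one missed | 84 | 74–94 | 0 of 121 |
| Week 42, Week 48 missed, Week 56 | 98 | 88–108 | 93 of 121 |
| 8-weekly, one missed (Week 48 to 64 and later) | 112 | 102–122 | 121 of 121 |

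For the middle row, the gap falls short of 95 when the two deviations together shorten it by 4 to 10 days: 7+6+5+4+3+2+1 = 28 combinations, and 121 − 28 = 93. On the 6-weekly schedule two missed scans give 116–136 days, so the limit separates one from two there. A death, or progression on an unscheduled scan, less than 95 days after the last adequate scan does not meet the limit on either schedule.

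**Where the effect can start.** The earliest last adequate scan that can be affected is the start of the Week 42 window, day 294 − 5 = 289. In the SAP's months this is (289 + 1)/30.4375 = 9.5. The earliest event that can be lost is day 289 + 95 = 384, or (384 + 1)/30.4375 = 12.6 months. Month 6 is about Week 26, so the primary endpoint lies well before both.

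**The 12-month estimate.** No event before month 12.6 is lost, but the estimate can still change, in two ways.

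- *Smaller risk set.* Take 10 subjects with 8 early events, so the curve stands at 0.20. Subject A has a last adequate scan on day 294, misses Week 48 and has PD on day 392 (98 days). Subject B has PD on day 336. If A is kept, two are at risk on day 336 and the estimate is 0.20 × 1/2 = 0.10. If A is censored at day 294, B is alone and it is 0.00. With 7 early events and one further subject at risk, it is 0.30 × 2/3 = 0.20 against 0.30 × 1/2 = 0.15.
- *Curve ends early.* Suppose one subject is left at Week 48 (curve at 0.10), misses Week 56 and has PD at Week 64 (day 448, month 14.8). Kept: 10 events, and the curve falls to 0. Censored at day 336: 9 events, and the curve stays at 0.10 and ends at month 11.1. More generally, if the last subject at risk had the last adequate scan at Week 42 or 48, the curve ends between day 289 and day 341 (months 9.5–11.2).

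**Expected number affected.** Assumptions: each scan is missed or not evaluable with probability p, independently; windows are equally likely; PD is found at the next scheduled scan; PFS is exponential. Per subject:

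Σ over missed scan m, Week 48 to Week 96, of [S(m−1) − S(m+1)] × p(1−p)² × P(gap ≥ 95)

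where m−1 and m+1 are the scheduled scans on either side of m. First term for p = 0.10 with the 2.7-month median of the earlier phase 3 study (Protocol Section 2.3.2.1): S(294) = 0.0838 and S(392) = 0.0367, so 0.0471 × 0.10 × 0.81 × 93/121 = 0.0029. The whole sum is 0.0102.

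| p | 2.7-month median: per subject, per 10, chance of at least one | 32% at 6 months (SAP Section 1.3): same |
|---|---|---|
| 5% | 0.0057, 0.06, 6% | 0.0108, 0.11, 10% |
| 10% | 0.0102, 0.10, 10% | 0.0194, 0.19, 18% |
| 20% | 0.0161, 0.16, 15% | 0.0307, 0.31, 27% |

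Neither curve fits both planning figures: a 2.7-month median implies 0.5^(6/2.7) = 21% at 6 months, and 32% at 6 months implies a median of 3.65 months. The tail is therefore uncertain.

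**The case against.** The strongest reply is that the table does define the gap: 95 days is the definition and the count is only an example. On that reading 102 to 122 days without an adequate scan is a long gap on any schedule, and the natural censoring date is the last adequate assessment before it. That reading is tenable, and a programmer could adopt it without strain. But the parenthesis derives the limit from two 6-week intervals, and the date column is written solely in terms of two missing assessments. The row supports both readings after Week 48 and chooses neither.

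Three further points stand. The sum is right, so a reader who infers that 95 days was miscalculated is mistaken; the fault is the mismatch with the later schedule. Footnote 1 is not marked on this row, so the view that one not-evaluable scan has the same effect as a missed one holds only if its definition of adequate is carried over, which is reasonable but inferred. And the effect is small: scans on suspected progression, deaths, late make-up scans and new therapy would all lower the figures above.

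**Conclusion.** The row is wrong as written for the 8-weekly period. It is an internal inconsistency of minor severity.

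A reader might infer that the primary result is at risk. The documents do not support that: no censoring date before day 289 (month 9.5) can move, so the 6-month test and the 3-, 6- and 9-month rates are untouched. The opposite inference, that the 12-month rate is safe because no earlier event is lost, also fails, for the risk-set reason shown above.

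What can change is late descriptive output with no formal test attached: event and censoring counts, the tails of the IRC and Investigator PFS curves, the 12-month estimate and the DoR listing. The expected size is 0.06 to 0.31 of 10 subjects, with a 6 to 27% chance of at least one. This rests on the assumed 5 to 20% missed or not-evaluable rate and on exponential PFS.

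**What to change.** Rewrite the one row so that both conditions must hold:

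- **Trigger.** PD or death occurs at least 95 days after the last adequate assessment (counted from C1D1 if there is no adequate post-baseline assessment, as now) and after two or more consecutive scheduled assessments, on the schedule in force and with windows closed, without an adequate assessment. Not evaluable counts as missing.
- **Censoring date.** The last adequate assessment before that run, or C1D1 if there is none.
- **Scope.** IRC PFS, Investigator PFS and DoR.

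Both parts are needed to leave early cases alone. For every last adequate day from 0 to 288, at least two later scan windows have closed 95 days on, so the combined rule treats these cases as the present limit does; the first exception is day 289. A count alone would not: with a last adequate scan on day 42, Weeks 12 and 18 missed and death on days 132–136, the gap is 90–94 days, kept now but censored by count.

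The C1D1 clause matters too. A baseline scan may be 21 days before C1D1. If it were taken as the last adequate assessment, a death on days 90–94 with Weeks 6 and 12 missed would be 111–115 days out and censored, whereas it is kept now.

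Cost: one SAP table row and its programming, best settled before late data are analysed.

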### 5.3.1.1. Sensitivity analysis

The primary efficacy endpoint may be analyzed based on the PPS using the same method in the primary analysis.

### 5.3.2. Secondary efficacy endpoints

#### 5.3.2.1. Overall survival (OS)

Overall survival is defined as the time from C1D1 to the date of death due to any cause. Subjects will be followed for survival until all subjects have either died, withdrawn consent, are lost to follow-up, or up to 24 months after last subject enrolled, whichever occurs first. Subjects who are alive at the analysis cutoff date will be censored at the date of last contact.

Kaplan-Meier estimates of OS will be presented, including estimates of the median and other quantiles, as well as individual time points (e.g., 3-month, 6-month, and 12-month rates).

Duration of follow-up defined as the time from C1D1 to the earliest of last known alive date or data cutoff date will also be analyzed in the same way as OS. Subjects with documentation of death on or before the time of data cutoff will be censored at the date of death.

#### 5.3.2.2. PFS per investigator

PFS per investigator is defined as the time from C1D1 to the date of first documentation of disease progression as assessed by investigator per RECIST v1.1 or death due to any cause, whichever occurs first.

The same censoring rules as the primary endpoint of PFS will be applied to PFS per Investigator.

The analysis for PFS per investigator will be like PFS by IRC (see [Section 5.3.1](#)).

#### 5.3.2.3. Objective response (OR)

Objective response is defined as confirmed CR or PR per RECIST v1.1. OR will be analysed by IRC as primary analysis and by Investigator as sensitivity analysis.

Objective response rate (ORR) will be derived from the best overall response (BOR). BOR is defined as the best time point response that a subject achieves during the course of the study, with the response ranked according to the following order (from best to worst): CR>PR>SD>PD>UNK>Other (including Not Evaluable and Not Assessed). The number and proportion of subjects by category of BOR will be presented. The number and proportion (95% CI based on Clopper-Pearson method) of subjects who achieved OR will be presented. If the subject has no response assessment, it will be treated as a non-responder in the analyses.

Per RECIST v1.1, SD that occurred within <38 days from C1D1 is assigned as UNK (6 weeks minus 5 days per protocol allowed visit window). In addition, the BOR of CR or PR requires a confirmation scan. The specific confirmation rule can be found in Table 3 of CSP.

The waterfall plot of the best % change from baseline in target lesion measurement (sum of diameters) will be presented. The target lesions post-baseline vs. baseline have to be matched in order to calculate % change, except for the case where lesions disappeared (Absent or Too Small to Measure) or merged or split. If the lesion status is “Absent,” 0 mm will be used as the measurement; if the lesion status is “too small to measure,” 5 mm will be used per RECIST v1.1 guidance.

The swim lane plot of treatment duration per subject will be presented. Treatment ongoing status will be marked at the end of the lane. The BOR will be marked in colors. The swim lane plot will be based on ITT set.

A summary of best overall response will be listed.

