18. Tumor assessments will include all known or suspected disease sites. CT imaging of the chest, abdomen, and pelvis (Torso) with contrast should be performed at baseline and on study. For subjects with allergy to IV iodine contrast, CT chest without IV contrast and MRI abdomen with IV contrast should be performed at baseline and on study. Brain scans with CT or MRI should be performed at baseline in subjects with known treated brain metastases and on study at the same imaging time points as Torso imaging. Bone scans will be performed at baseline if disease is suspected and on study at the same imaging time points as Torso imaging. Radiographic assessment (CT or MRI) for evaluation of disease response to be conducted at Screening (Day -21), every 6 weeks beginning at C1D1 (± 5 days) for the first 8 assessments (ie, through week 48), and then every 8 weeks (± 5 days) from C1D1, thereafter independent of dose delays and/or dose interruptions, and/or at any time when progression of disease is suspected. All scans obtained will be sent to the IRC, as detailed in the site-specific Imaging Core Manual.

19. Extent of disease will be assessed based on RECIST v1.1.
20. If a subject goes off treatment for reasons other than disease progression, response assessments will be conducted at the EOT Visit and every 6 weeks (± 5 days) for the first 8 assessments (ie, through week 48), and then every 8 weeks (± 5 days) thereafter until withdrawal of consent, disease progression, death, the subject is lost to follow-up, or until the end of study/study termination.
21. EORTC-QLQ-C30 and EORTC-QLQ-BIL21, to be conducted pre-dose on C1D1. After EOT visit, the HRQOL will be conducted every 12 weeks until the start of new anticancer therapy.
22. EQ-5D-5L to be conducted pre-dose on C1D1, C3D1, and at the EOT visit.
23. Adverse events will be graded according to the National Cancer Institute Common Terminology Criteria for Adverse Events v5.0. After informed consent has been obtained but prior to initiation of study drug, only SAEs caused by a protocol-mandated intervention should be reported. After initiation of study drug, all AEs and SAEs regardless of attribution will be collected. Any SAEs that are assessed as related to study treatment that occur >28 days post-treatment also are to be reported.

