7.2. Methods and measurement times

The efficacy of ivosidenib will be evaluated by assessing response to treatment according to RECIST v1.1 ([Eisenhauer *et al*, 2009](#)) ([Appendix 3](#)).

Radiographic assessments (CT or MRI) to obtain tumor measurements are to be conducted at Screening (Day -21), every 6 weeks (± 5 days) for the first 8 assessments (i.e., through week 48), and every 8 weeks thereafter (± 5 days) from C1D1, independent of dose-delays and/or dose interruptions, and/or at any time when progression of disease is suspected. CT imaging of the chest, abdomen, and pelvis (Torso) with IV contrast should be performed at baseline and on study. For subjects with allergy to IV iodine contrast, CT of the chest without IV contrast and MRI of the abdomen with IV contrast should be performed at baseline and on study. Brain scans with CT or MRI should be performed at baseline in subjects with known treated brain metastases and on study at the same imaging time points as Torso imaging. Bone scans will be performed at baseline if disease is suspected and on study as appropriate as the same imaging time points as Torso imaging. Any ancillary findings on the radiographic assessments will be communicated to the appropriate physician for notification to the subject.

The same method (CT or MRI) should be used consistently for any given subject. For subjects permitted to continue on ivosidenib beyond documented radiographic progression, a new baseline imaging assessment will not be required, and the imaging assessments will continue on the current schedule. For subjects who discontinue study drug for reasons other than disease progression, a response assessment will be conducted at the EOT Visit. Subjects who have not experience disease progression and are alive by EOT will enter PFS follow-up with the same schedule of assessments as before study treatment discontinuation, until documented disease progression, death, start of subsequent anticancer therapy, withdrawal of consent, loss to follow-up, or until the end of study/study termination.

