The best overall response is the best response recorded from the start of the study treatment until the end of treatment taking into account any requirement for confirmation. On occasion a response may not be documented until after the end of therapy so protocols should be clear if post-treatment assessments are to be considered in determination of best overall response. Protocols must specify how any new therapy introduced before progression will affect best response designation. The patient's best overall response assignment will depend on the findings of both target and non-target disease and will also take into consideration the appearance of new lesions. Furthermore, depending on the nature of the study and the protocol requirements, it may also require confirmatory measurement. Specifically, in non-randomised trials where response is the primary endpoint, confirmation of PR or CR is needed to deem either one the 'best overall response'.

Time point response

It is assumed that at each protocol specified time point, a response assessment occurs. [Table 1](#) provides a summary of the overall response status calculation at each time point for patients who have measurable disease at baseline.

Table 1: Time point response: patients with target (\pm non-target) disease

Target lesions	Non-target lesions	New lesions	Overall response
CR	CR	No	CR
CR	Non-CR/non-PD	No	PR
CR	Not evaluated	No	PR
PR	Non-PD or not all evaluated	No	PR
SD	Non-PD or not all evaluated	No	SD
Not all evaluated	Non-PD	No	NE
PD	Any	Yes or No	PD
Any	PD	Yes or No	PD
Any	Any	Yes	PD

CR = complete response, PR = partial response, SD = stable disease, PD = progressive disease, and NE = Not evaluable

When patients have non-measurable disease only (therefore non-target), [Table 2](#) is to be used.

Table 2: Time point response: patients with non-target disease only

Non-target lesions	New lesions	Overall response
CR	No	CR
Non-CR/non-PD	No	on-CR/non-PD ¹
Not all evaluated	No	NE
Unequivocal PD	Yes or No	PD
Any	Yes	PD

CR = complete response, PD = progressive disease, and NE = Not evaluable.

1 = 'Non-CR/non-PD' is preferred over 'stable disease' for non-target disease since SD is increasingly used as endpoint for assessment of efficacy in some trials so to assign this category when no lesions can be measured is not advised.

Missing assessments and inevaluable designation

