#### 5.3.2.4. Duration of response (DoR)

A responder is defined as a subject who achieved objective response (see [Section 5.3.2.3](#)). Among the responders, DoR in months will be calculated from the date of the first occurrence of response to the date of first documented disease progression or death, whichever comes earlier. See [Table \(5.3.1\) 1](#) for the censoring rules.

Duration of response = (Earliest Date of Death/Progression – Date of First Confirmed PR/CR + 1)/30.4375.

DoR may be analysed by IRC as primary analysis and by Investigator as sensitivity analysis. If there are at least 5 responders, Kaplan-Meier plot of DoR may be generated.

Listing on DoR will be provided for responders.

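### SAP 5.3.2.3 sets no cut at first progression for best overall response, so a confirmed response read after progression could count toward ORR and carry a negative duration of response

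*SAP*

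**What the plan says.** SAP 5.3.2.3 derives ORR from BOR, and BOR is defined as follows: "BOR is defined as the best time point response that a subject achieves during the course of the study". Responses are ranked from CR down through PR, SD and PD. The section adds two qualifiers. SD needs at least 38 days from C1D1, and "In addition, the BOR of CR or PR requires a confirmation scan", with the rule taken from Table 3 of the RECIST appendix (Protocol Appendix 3). Neither qualifier refers to an earlier PD or to a new anticancer drug.

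SAP 5.3.2.4 computes DoR as ("Earliest Date of Death/Progression – Date of First Confirmed PR/CR + 1") divided by 30.4375. It borrows the censoring rules of Table (5.3.1) 1, including the one for alternate anticancer therapy. The BOR section does not cite that table.

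Protocol 8.10.1.2 permits ivosidenib after radiographic progression under stated conditions. Protocol 7.2 keeps the scan schedule running and the original baseline in force: "For subjects permitted to continue on ivosidenib beyond documented radiographic progression, a new baseline imaging assessment will not be required". The same section says the independent review does not inform treatment decisions, and 7.2.1 sends all scans to the Independent Radiology Center (IRC).

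Protocol Appendix 3 gives BOR a different window, from start to end of treatment, also without a cut at PD. It adds: "Protocols must specify how any new therapy introduced before progression will affect best response designation". Neither document makes that specification for BOR.

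**The concern.** PFS and DoR stop at the first PD. BOR, as written, does not. The two rules meet in any subject who is still being scanned after PD, and the design provides for such subjects in two ways. One is the decision to treat beyond progression. The other needs no decision: a subject with PD by the IRC but not by the Investigator simply carries on. Because the IRC read is the primary analysis for objective response, the second way matters, and the SAP already plans a summary of concordance between the two assessors.

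BOR is a maximum over the window, so a longer window can add responders but never remove them. Any distortion of ORR is therefore upward. The DoR and time-to-response entries for such a subject would start from a date later than the PD that ended the subject's PFS. Someone would then have to choose a rule with the data in hand, in an open-label trial of about 10 subjects.

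**Working it through.** **The plan's own figure.** The documents state no number for BOR, ORR or DoR. The only related figure is the 84% power for the 6-month PFS rate (SAP 1.3), which reproduces:
- Evaluable subjects: 10 × 0.9 = 9. Reject if 2 or more are progression-free.
- Under 2.6%: P(X ≥ 2 of 9) = 0.0216. Under 32%: P(X ≥ 2 of 9) = 0.837.

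BOR does not enter this calculation, so the point cannot change it.

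**Can a PR-size reading follow a PD?** In Appendix 3, PD is judged from the smallest sum on study (at least 20% and 5 mm), and PR from the baseline sum (at least 30% down). Take assumed sums in mm of 100 at baseline, 75 at week 6, 91 at week 12 and 68 at weeks 18 and 24.
- Week 12: (91 - 75)/75 = +21%, +16 mm: PD.
- Weeks 18 and 24: (68 - 100)/100 = -32%: PR size, seen twice.

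The sequence is possible on size alone. Table 3 of Appendix 3 has no row that starts with PD. It neither excludes the later PR-PR pair nor assigns it a result.

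**DoR under the SAP formula.** Scans are every 6 weeks ± 5 days through week 48. The study day at week w is 7w + 1.

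| First PD | First PR | DoR (months) |
|---|---|---|
| Week 6, Day 43 | Week 12, Day 85 | (43 - 85 + 1)/30.4375 = -1.35 |
| Week 12, Day 85 | Week 18, Day 127 | (85 - 127 + 1)/30.4375 = -1.35 |
| Week 6, Day 43 | Week 18, Day 127 | (43 - 127 + 1)/30.4375 = -2.73 |

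With the visit windows, adjacent scheduled scans are 42 ± 10 days apart, that is 32 to 52 days. DoR then runs from (-32 + 1)/30.4375 = -1.02 to (-52 + 1)/30.4375 = -1.68 months. It is negative throughout.

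**ORR at N = 10** (Clopper-Pearson, as SAP 5.3.2.3 specifies).

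| Responders | ORR | 95% CI |
|---|---|---|
| 0/10 | 0% | 0-30.8% |
| 1/10 | 10% | 0.3-44.5% |
| 2/10 | 20% | 2.5-55.6% |

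Each post-progression responder moves the result down one row of this table, by 1/10 = 10 points.

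**New anticancer therapy, passages side by side.**
- Scanning in PFS follow-up ends at new therapy: Protocol 4.1.1, Protocol 7.2, footnote 3 of Table (4.1.2) 1, and SAP 1.2.1.
- Other anticancer therapy is not permitted during the study: Protocol 6.3.3.
- BOR ends with treatment: Protocol Appendix 3.
- No such stop: footnote 20 of the same schedule table, where off-treatment scans run "until withdrawal of consent, disease progression, death, the subject is lost to follow-up" or the end of the study, and the BOR definition in SAP 5.3.2.3.

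If a first response were read only after a new drug, with no earlier PD, Table (5.3.1) 1 would censor DoR at the last adequate assessment before that drug. That date precedes the response, so the result is again negative.

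**The case against.** The strongest reply is that the route is narrow. Objective response must be confirmed and must follow RECIST v1.1. Under Table 1 of Appendix 3, a time point with a new lesion is PD whatever the target lesions show, so progression by new lesions cannot readily turn into PR. What remains is PD by size from nadir, or non-target PD that reverses, followed by a confirmed fall to at least 30% below baseline. Treatment beyond progression also ends on clinical deterioration or continued radiographic progression. All of this stands, and it makes the event uncommon. It does not make the rule right, because nothing in the BOR text excludes the case.

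Second, first documented progression in the DoR text could be read as the first PD after the response, and DoR would then be positive. That reading is open in the prose, but the formula takes the earliest date. Under that reading the subject would still count as a responder.

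Third, an IRC charter may stop reads at PD. It is not among the documents, and it would not govern the Investigator analysis.

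Fourth, the endpoints are secondary and descriptive, DoR and time to response are listed by subject, and an odd value would be noticed among about 10 subjects. That is correct and limits the harm. It also means the rule would be settled after the data were seen.

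A reader might also infer that responses on a later drug would routinely count. The documents do not support that. Several provisions stop scanning at new therapy, and Appendix 3 ends BOR with treatment. Only footnote 20 and the SAP window leave the door ajar.

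**Conclusion.** The point holds as a defect in a stated rule. Read literally, SAP 5.3.2.3 could count a confirmed PR or CR that follows the same assessor's first PD, and SAP 5.3.2.4 would then give it a negative DoR: -1.02 to -1.68 months for adjacent scheduled scans, and more negative for a later response. Each case adds 10 percentage points to ORR at N = 10, always upward.

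This rests on two assumptions: such a response is observed and confirmed, and the IRC (or the Investigator) goes on reading after PD. The documents give no frequency for either, so they do not support saying that ORR will be inflated. New anticancer therapy is a secondary gap that comes down to an inconsistency between passages.

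The SAP window also differs from the one in Appendix 3, although SAP section 7 records no change from the protocol. The primary endpoint and its 84% power are unaffected. The change is worth making because it is cheap and should be settled before response data are analysed.

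**What to change.** In SAP 5.3.2.3, derive BOR from assessments after C1D1 up to and including the first documented PD by the same assessor (IRC or Investigator), or up to the last adequate assessment before alternate anticancer therapy, whichever is earlier. The confirmation scan must fall in the same window. Apply that window to objective response, time to response and DoR. This removes every zero or negative DoR arising from the two routes above. Readings after the cut can still be listed, labelled as such.

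Reconcile the SAP window with the one in Appendix 3, and record the departure in SAP section 7 if one remains. Footnotes 3 and 20 of Table (4.1.2) 1 must also be reconciled on whether scans continue after new anticancer therapy. The SAP cut works whichever way that is resolved.

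The cost is one sentence of SAP text, one programming filter and an editorial correction to the schedule footnotes. No extra data, visits or subjects are needed.
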